### **2.3.3 INPATIENT NEUROIMAGING SCHEDULE (PHASE B)**

Based on the screening visit (Phase A), consenting volunteers will be scheduled for study Phase B (inpatient visit to the MCRU at the NIH Clinical Center), preceded by up to 5 days of dietary stabilization as described above. This phase (B) of the study will occur as up to 6 contiguous inpatient days (depending on facility availability). To control for the impact of gonadal hormones on food intake, every effort will be made so that female subjects of reproductive potential will be admitted during the follicular phase of their menstrual cycle.

Following admission for Phase B, volunteers will undergo metabolic measurements consisting of: body weight and height; measurement of body composition (e.g., dual energy x-ray absorptiometry (DEXA), air-displacement plethysmography (BodPod)) and they will complete a battery of self-report questionnaires and computer tasks related to mood, stress, thoughts about food and eating, and self-control. Female subjects of reproductive potential will also complete a urine pregnancy test on Day 1 of the inpatient visit and interviewed about the possibility of pregnancy. Positive test results will preclude subjects from further participation. The purpose of these measurements is to facilitate examination of exploratory aims by providing a comprehensive assessment of whole-body composition in the subjects, as well as measures of cognitive processes that subserve typical food intake and feeding behaviors. The baseline measurements will then be compared with similar measurements during the 1-year follow-up. Except where noted, subjects will be provided a standard breakfast, lunch and dinner (approximately 50% calories from carbohydrate, 35% from fat and 15% of calories from protein) along with coffee/tea or diet soda in accordance with their usual intake.

Subjects will complete an overnight fast prior to PET scanning for all inpatient visits. Each subject will complete two PET sessions under the following conditions: (1) fasted state with [F]fallypride, (2) [C]raclopride while fasted and post-milkshake challenge. The order of the PET scans using [F]fallypride and [C]raclopride sessions will be pseudo-randomized (i.e., random scan order will be requested but final schedule ultimately depends on PET department scheduling/capabilities of radiopharmacy production). Prior to each PET scan session (i.e., fasted state), a blood sample will be collected via venipuncture to enable measurement of circulating satiety hormones. Additionally, subjects will be asked to report subjective stress levels and craving for food at this time, measured using a Visual Analog Scales (VAS).

PET scanning will begin in the morning, and, as diurnal variation may affect radioligand binding potential, time of day will be consistent across PET conditions. The [F]fallypride scan session is expected to last approximately 3.5 hours, and subjects will be provided two scheduled breaks from scanning. Within the [C]raclopride session, both [C]raclopride scans will be about 60 min in length each, separated by a rest period of at least 60 minutes during which participants will be encouraged to void to empty the bladder, and consume 250 mL of milkshake. The second dose of [C]raclopride will be administered at least 60 min following the baseline dose. At three times (before, midway through (during a scheduled break) and near completion of Fallypride and Raclopride scan sessions), a nurse will draw a blood sample from subjects via catheter to assess any change in post-absorptive signals. Participants will be encouraged to drink water at the conclusion of each scan. An *ad libitum* test meal will be provided following completion of all scan days.

Participants will also undergo up to two MRI sessions during their inpatient stay. Prior to one scan, participants will undergo a blood draw to provide a research sample as well as blood for genetic testing. Each scan will be no more than 2 hours in duration and may consist of structural

and functional brain imaging as well as measurement of neurometabolic profile, depending on facility availability.

While at the MCRU, after an overnight fast, the participant may undergo indirect calorimetry to assess resting energy expenditure. The participant may be dosed with doubly labeled water and initial urinary samples may be collected. A member of the research team will instruct the participant on procedures for urinary collection, activity and weight monitoring during the outpatient phase (Phase C). The participant may be provided with accelerometers and a scale to track body weight at home. A member of the research team will discuss with the subject to schedule any remaining neuroimaging sessions, if applicable. Female participants will be scheduled to complete scanning, ideally within the follicular phase of their menstrual cycle to control for the effects of gonadal hormones on feeding behavior. Because inter-individual variability in menstrual cycle length has been reported, follicular phase will be adjusted by the average length of each woman's menstrual cycle. On average, the follicular phase in adult women is 15 days in length, so every effort will be made to admit women for their inpatient stay within 10 days of the first day of menstruation.

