#### **2.3.5 ONE-YEAR FOLLOW-UP (PHASE D)**

In order to investigate the correlates of brain dopamine D2BP such as free-living physical activity, ad libitum meal consumption, and body weight and brain changes over a longer-term, participants may be asked to provide select data intermittently over the following 12 months and return to the clinical center for more comprehensive repeat assessment.

For the 12-month follow up period (Phase D), subjects may be asked to use the provided scale to log daily weights over 12 months. Subjects may also be provided with commercial activity monitors to track daily physical activity for 12 months. Four times over the year, for a duration of 7 days each collection period, subjects may be mailed research-grade activity monitors (actigraphy) for daily use and be instructed to return the devices by mail at the end of 7 days. Subjects may also be asked to complete and return surveys/questionnaires (concerning eating behavior, and activity) during quarterly collection periods.

At 12 months ( $\pm$  2 months) following completion of the inpatient PET portion, subjects may be invited back to the NIH Clinical Center to complete one outpatient visit consisting of repeat MRI session, fasting research blood sampling, body composition measurement (e.g., DEXA, BodPod, BIS), computer tasks and self-report questionnaires. Subjects would be provided with lunch during their 1-year follow up visit.

To the extent possible, portions of the follow-up visit may be completed remotely and/or via telehealth appointment.

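### Phase B targets the follicular phase for women, but the one-year visit it will be compared with has no cycle-phase rule, so exploratory one-year change in women partly reflects cycle phase

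*Combined protocol and SAP*

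**What the plan says.** Section 2.3.3 sets the baseline rule: "every effort will be made so that female subjects of reproductive potential will be admitted during the follicular phase of their menstrual cycle". The reason given there is the effect of gonadal hormones on food intake. Later in the section, scanning of women is to fall "ideally within the follicular phase of their menstrual cycle to control for the effects of gonadal hormones on feeding behavior". The working figures follow: "On average, the follicular phase in adult women is 15 days in length", and "every effort will be made to admit women for their inpatient stay within 10 days of the first day of menstruation", with the phase adjusted to each woman's average cycle length. The rule is best effort throughout.

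After describing the baseline body-composition, questionnaire and task measurements, section 2.3.3 adds: "The baseline measurements will then be compared with similar measurements during the 1-year follow-up".

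Section 2.3.5 describes the other side of that comparison. At 12 months plus or minus 2 months, "subjects may be invited back to the NIH Clinical Center to complete one outpatient visit consisting of repeat MRI session, fasting research blood sampling", followed by body composition, computer tasks and questionnaires. It sets no cycle-phase condition and does not ask for cycle day to be recorded. Section 4 contains no analysis of one-year change and no cycle-phase covariate.

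**The concern.** The sponsor judged cycle phase important enough to schedule around at baseline, then planned a within-person comparison with a visit whose phase is left to chance. Had both visits been unscheduled, phase would add noise but would tend to cancel in the mean change. With baseline aimed at one phase, a follow-up in another phase differs from it in the same direction each time.

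One-year change in women could therefore carry a shift that men do not have. It could be read as change over the year, or as a sex difference in change, and it would add scatter to correlations between baseline D2BP and later change. Measures taken once at the visit are the exposed ones. The example blood panel in Table 3 includes FSH, LH and estrogen, and section 3.3 repeats research blood at one year.

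**Working it through.** The plan states no figure for this mismatch, so there is none to reproduce.

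**Inputs from the protocol**
- Follicular phase: 15 days on average (section 2.3.3).
- Admission within 10 days of the start of menstruation; stay of up to 6 contiguous days (section 2.3.3).
- One-year window: plus or minus 2 months (section 2.3.5).
- Core sample 39 (section 2.1), about half women (section 7.1): 39 / 2 = 19.5, about 20.

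**Assumptions not in the documents**
- Cycle length L = 28 days, range 24 to 35.
- The one-year visit falls on a random cycle day.
- All women cycle naturally and attend, unless stated otherwise.
- A phase effect of d standard deviations of the change score.

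**Step 1: is the baseline rule coherent?** Admission on cycle day 10 plus 6 inpatient days ends on day 10 + 6 - 1 = 15, the stated follicular length. It is coherent for a 6-day stay.

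**Step 2: share out of phase at one year.** Share = 1 - 15/L.
- L = 28: 13/28 = 46%.
- L = 24: 37.5%; L = 35: 57%.
- Holding the non-follicular part at 13 days instead (13/L): 54% at L = 24, 37% at L = 35.

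**Step 3: numbers of women.** 20 × 0.464 = 9.3, about 9 of 20. As a share of all participants, 0.5 × 0.464 = 23%. If 25% or 50% of women used hormonal contraception, the share of women falls to 0.75 × 0.464 = 35% or 0.50 × 0.464 = 23%.

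**Step 4: shift in mean change.** With baseline in phase, the shift in women is 0.464 × d, and half of that in the whole sample.
- d = 0.3: 0.14 SD in women, 0.07 SD overall.
- d = 0.5: 0.23 SD in women, 0.12 SD overall.
- Added variance in women is 0.464 × 0.536 × d², which is 0.022 at d = 0.3 and 0.062 at d = 0.5 (in SD squared).

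**Step 5: effect on a nominal 5% paired test.** Simulation: change scores standard normal with no true change, 46% of 20 women shifted by d, two-sided t test.

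| Assumed d | 20 women | All 39 |
|---|---|---|
| 0.1 | about 5% | about 5% |
| 0.3 | about 9% | about 7% |
| 0.5 | about 15% | about 10% |

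Drawing each woman's phase at random, rather than fixing the count at 9 of 20, puts the last row nearer 16% and 11%.

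**Step 6: room in the window.** Four months is about 4 × 30.4 = 121.6 days, or 121.6 / 28 = 4.3 cycles (3.5 at 35 days, 5.1 at 24 days). Several eligible periods exist for each woman.

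**The case against.** The case for leaving the plan alone has real substance.

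- **Status of the data.** Section 1.3 presents the exploratory measures as hypothesis-generating and possibly incomplete, and section 2.3.5 makes the one-year visit optional. Section 4 names no test of one-year change, so the rejection rates above describe a test the plan does not specify. This stands, and it keeps the severity low.
- **Reach.** The only change outcome named in Exploratory Aim 3 is body weight, which is logged daily at home for 12 months (section 3.3.4). Activity is also tracked daily (section 3.3.3). The ad libitum meal, the direct measure of intake, is not among the procedures listed for the one-year visit, and functional MRI depends on facility availability. This also stands. The exposed measures are those taken once at the visit.
- **Size.** No phase effect is given, and at 0.1 SD the test is close to nominal. The documents are silent on hormonal contraception. Both points stand, so the bias can only be shown as a range.
- **Hormone assays.** FSH, LH and estrogen might help classify phase afterwards. But Table 3 is an example list and no such use is stated, so this is a possible rescue and not a plan.

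A reader might go further than the documents allow in three ways.

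- One might treat the 10-day admission window as the phase boundary. That gives 1 - 10/28 = 64% out of phase, about 13 of 20 women, and rejection rates up to 26% in women and 16% overall. But the window governs admission, the stated phase is 15 days, and a day-10 admission can put baseline measures on days 11 to 15. A one-year visit on those days is in phase.
- One might say that every woman starts in the follicular phase. The rule is only best effort, and the Table 1 caption lets Phase B be split into two or three visits or run to 11 inpatient days (10 + 11 - 1 = day 20). A baseline outside the phase offsets part of the shift. If an assumed 90% were in phase at baseline, the mean shift would be 0.464 - 0.10 = 0.364 of d.
- One might infer that the primary aims are compromised. PET is not repeated at one year, so they are not.

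**Conclusion.** The gap is real and lies within the plan's own text: cycle phase is targeted at one end of a planned comparison and left open at the other. The central figure is 46% of naturally cycling women who attend, which rests on the protocol's 15-day phase, a 28-day cycle and a random visit day. In count it is about 9 of 20 women, given full attendance and no hormonal contraception.

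The consequence for inference is conditional. If phase shifts a measure by 0.3 to 0.5 SD of the change score, a nominal 5% paired test would reject in about 9 to 15% of trials in 20 women and 7 to 10% in all 39. At 0.1 SD there is almost no effect. The direction is mainly one-sided, to the extent that the baseline rule is met.

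This is a cheap improvement to exploratory follow-up, of low severity.

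**What to change.** In section 2.3.5, add that the one-year visit of women of reproductive potential will be scheduled by the existing Phase B cycle rule, on the same best-effort basis and inside the existing 12 months plus or minus 2 months. Record cycle day and hormonal contraceptive use at both the Phase B measurements and the one-year visit. In section 4, add a sensitivity analysis of one-year change that keeps, among women, only those whose two visits match on phase.

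To the extent that the rule is met at both visits, the expected out-of-phase share falls from about 46% to about zero. Where it is not met, the recorded cycle day identifies the visits concerned.

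The cost is one scheduling sentence, two recorded items per visit and slightly less scheduling freedom. The items should be collected at the visits, because the plan gives no other way to establish phase afterwards.

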#### **2.3.4 POST-ADMISSION OUTPATIENT MONITORING (PHASE C)**

In order to examine dopamine D2BP in relation to free-living activity levels and energy balance, participants may be asked to collect daily urine samples as well as monitor weight and activity (via NIH-provided Wi-Fi-enabled, commercial digital scale for home use and research-grade actigraphs) for a predetermined number of contiguous days post discharge. The subjects would be provided equipment for the collection and shipment of urine samples, which will be collected at home for a predetermined number of days following the doubly labeled water dose. Actigraphs would be returned to NIH at the end of this period.

#### **2.3.5 ONE-YEAR FOLLOW-UP (PHASE D)**

In order to investigate the correlates of brain dopamine D2BP such as free-living physical activity, ad libitum meal consumption, and body weight and brain changes over a longer-term, participants may be asked to provide select data intermittently over the following 12 months and return to the clinical center for more comprehensive repeat assessment.

For the 12-month follow up period (Phase D), subjects may be asked to use the provided scale to log daily weights over 12 months. Subjects may also be provided with commercial activity monitors to track daily physical activity for 12 months. Four times over the year, for a duration of 7 days each collection period, subjects may be mailed research-grade activity monitors (actigraphy) for daily use and be instructed to return the devices by mail at the end of 7 days. Subjects may also be asked to complete and return surveys/questionnaires (concerning eating behavior, and activity) during quarterly collection periods.

At 12 months ( $\pm$  2 months) following completion of the inpatient PET portion, subjects may be invited back to the NIH Clinical Center to complete one outpatient visit consisting of repeat MRI session, fasting research blood sampling, body composition measurement (e.g., DEXA, BodPod, BIS), computer tasks and self-report questionnaires. Subjects would be provided with lunch during their 1-year follow up visit.

To the extent possible, portions of the follow-up visit may be completed remotely and/or via telehealth appointment.

### **3. Analytical Procedures**

#### **3.1 PET imaging**

##### **3.1.1 PRE-SCAN PROCEDURES**

1. *Fasting.* Subjects will be required to complete an overnight fast prior to all PET scan sessions.
2. *Review of scanning protocol.* A member of the research team will review the procedures to be completed during the scan session and answer any questions from the subject. Subjects will be reminded that they will be provided rest periods throughout the session.
3. *Blood sampling.* A venous blood sample may be collected via catheter ~30 minutes prior to the start of each PET scan for assessment of metabolite and hormone concentrations. A second blood sample may be collected during a scheduled break in the Fallypride scan as well as immediately prior to the second Raclopride injection. A final blood sample will be collected near the conclusion of both scan sessions.

##### **3.1.2 PET DATA ACQUISITION: [18F]FALLYPRIDE AND [11C]RACLOPRIDE/MILKSHAKE-CHALLENGE**

Dopamine type-2 receptor availability will be evaluated by PET scans that will be performed on a dedicated head scanner, the High-Resolution Research Tomograph (HRRT) with ~2.5 mm resolution.  $[^{11}\text{C}]$ raclopride and  $[^{18}\text{F}]$ fallypride are the radiotracers that will be used to determine dopamine D2 receptor availability.  $[^{18}\text{F}]$ fallypride is a selective, high-affinity dopamine D2 receptor antagonist, and  $[^{11}\text{C}]$ raclopride represents an alternative dopamine D2 receptor antagonist with moderate affinity.  $[^{18}\text{F}]$ fallypride is administered under the authority of an IND from the FDA #70,046;  $[^{11}\text{C}]$ raclopride is administered under IND #54,135. Both INDs are sponsored by the NIH Clinical Center, with [name], Director of Office of Research Support and Compliance (ORSC), as the sponsor's authorized representative. Prior to each scan, a swimming-like cap with small light reflectors will be placed on the subject's head. The cap is used to monitor the position of the subject's head during the scan. Information about head motion is used in the image reconstruction process to reduce the blurring effect of head movement on the PET images. Transmission scan information will be obtained over about 10 min with a  $^{137}\text{Cs}$  rotating pin source before each radiotracer injection to correct emission scans for attenuation. The radiopharmaceutical will be injected over a period of approximately 1-2 minutes using an FDA-approved infusion pump.

Upon completion of each scan, subjects will be asked to void to minimize radiation exposure to the bladder. We will control the environmental stimulation to the subjects to ensure that it is standardized for all subjects (noise kept to a minimum and room dimly lit). To estimate dopamine D2 receptor availability we will obtain the time-activity curves for both  $[^{11}\text{C}]$ raclopride and  $[^{18}\text{F}]$ fallypride in brain regions of interest, and tracer kinetics will be fit using a multi-compartment model with the cerebellum as a reference region.

Immediately following measurement of dopamine D2 receptor availability using  $[^{11}\text{C}]$ raclopride measured in a fasted state, an additional scan will be completed following the consumption of a milkshake (described in detail in the next section).

### **[F]fallypride PET Scan (Fasting):**

Subjects will begin preparation for scanning at ~ 9:00 AM when a fasting blood sample may be collected immediately following intravenous catheter insertion. The subject will be placed in the PET scanner following potential blood sampling, and the transmission (attenuation) scan will be performed. Subjects will receive an intravenous injection of approximately 5 mCi [F] fallypride. Acquisition of dynamic PET data will begin with radiotracer injection, lasting about 3.5 hours, separated by two scheduled breaks for the participant's comfort. Blood will be drawn via catheter during one of the scheduled breaks and again near the conclusion of the Fallypride scan.

### **[C]raclopride PET Scan (Fasting/Baseline):**

Subjects will begin preparation for scanning at ~ 9:00 AM when a fasting blood sample will be collected immediately following intravenous catheter insertion. Following blood sampling the subject will be placed in the PET scanner and the 10-minute transmission (attenuation) scan will be performed. Subjects will then be injected with approximately 20 mCi [C]raclopride. Acquisition of dynamic PET data will begin with radiotracer injection, lasting about 60 min.

### **Session Break + Milkshake:**

Upon completing the scan, subjects will be asked to void to minimize radiation exposure to the bladder. As described above, environmental stimulation will be controlled throughout the scan and standardized for all subjects.

Subjects will be provided a rest period following the initial PET scan. During this time, all subjects will be given a standard milkshake (approximately 250 cc of standardized milkshake [420 Cal]) to consume prior to the second PET scan. Subjects will be given 10 minutes to consume the milkshake and be asked to rate the pleasantness of the milkshake using a visual analog scale.

### **[C]raclopride PET Scan 2 (Test Scan):**

The second administration of [C]raclopride will occur approximately 30 minutes after the test meal is completed, which will be at least 60 min after completion of the first scan. PET scanning will begin with a blood sample collection via catheter, 10-minute transmission (attenuation) scan followed by the second intravenous bolus injection of approximately 20 mCi [C]raclopride, and dynamic PET data will be acquired for about 60 min. The binding potential of [C]raclopride for each scan will then be estimated by mathematical modeling, and dopamine release due to the test meal will be calculated from the percent reduction in binding potential between the two [C]raclopride scans (Wong and Brašić, 2001).

### **3.1.3 POST-SCAN PROCEDURE**

A third blood sample will be collected around the time of scan completion. Subjects will be evaluated for safety, and after their final PET scan session, the catheters are removed. All subjects will be asked to void to minimize radiation exposure to the bladder. Subjects will be encouraged to drink water upon completion of the scan. Subjects will be provided a eucaloric standard diet for the remainder of the day.

